### **Intervention Training and Fidelity**

CPS interventions were delivered by 6 "adherence facilitators" or "coaches" who were undergraduate research students enrolled in experiential research course at University of

Southern California (either in Department of Psychology or Department of Preventive Medicine). Coaches underwent a background check and completed the CITI Human Subjects Protection course, TrojanLearn Mandated Reporter course, and Praesidium Social Media Safety course, as recommended by the USC Department of Risk Management and Insurance. Coaches participated in 2 4-hour training sessions to learn the intervention, involving a combination of lecture and role-plays with feedback. Coaches participated in weekly group supervision with the PI, and all calls and texts were recorded, uploaded via HIPAA-compliant REDCap file upload link, and reviewed by PI using a fidelity checklist. Coaches completed a short survey after each contact to record whether the participant answered their call or text, whether they reported taking their medication since the last call, topics covered in the call, and any referrals given. Additional details about the CPS intervention can be found in prior publications [3,4].

## **Measures**

***Demographic Variables and Covariates.*** At pre-treatment, participants reported their age, sex assigned at birth, gender identity, racial identity, and ethnicity. They also reported their highest level of education, whether they had a job, and with whom they resided. In addition, they described their parents' highest level of education and completed the Family Affluence Scale II (FAS II; Boyce, Torsheim, Currie, and Zambon, 2006). The FAS II is a 4-item scale that can be summed, and used to categorize participants as low socioeconomic status (0-2), medium socioeconomic status (3-5), or high socioeconomic status (6-9). Previous studies have concluded that the FAS II is a valid and reliable measured of socioeconomic status (Liu et al., 2012). At follow-up, participants were asked to report on how COVID-19 had impacted their lives, using the COVID-19 Exposure and Family Impact Scales (Kazak et al., 2021). Finally, medication complexity will be calculated based on data in the electronic health record. We will follow the

procedures described by Lilly et al. (2013) in calculate a Medication Regimen Complexity Index (MRCI) calculated a score for the focal diagnosis and the non-focal diagnosis.

### ***Primary Outcomes: Adherence Dependent Variables***

**Self-Reported Adherence.** In this study, medication adherence over the past 3 months was measured by a 3-item visual analogue scale (VAS) developed by Walsh, Dalton, and Gazzard (1998). The VAS uses percentage scales that contains the percent (%) value from 0 to 100 in which each point on the scale suggests the percent of time of medication adherence within a specified duration of time: 0% would mean “none of the time” or “never”; 50% would mean half of the time; 100% would mean “all of the time” or “always”, and numbers in between would mean amounts between “never” and “always” (Walsh, Dalton, & Gazzard, 1998). For each time frame, three visual analogue scales are provided, assessing 1) the percentage of the time patients took their medicine, 2) the percentage of the time patients took all the doses for the day, and 3) the percentage of the time patients took their medicine according to the directions (Walsh, Dalton, & Gazzard, 1998). Administering self-report adherence surveys by computer may decrease social desirability bias (Stirratt et al., 2015).

**MEMS Caps Adherence.** Participants (and caregivers, in the case of minor participants) will be oriented to using MEMS caps for one of the medications they take daily of their focal diagnosis (i.e., immunosuppressant for transplant, antiepileptic drug for epilepsy, hydroxyurea for sickle cell disease, metformin for type 2 diabetes). Microelectronic circuitry records the dates and times the caps are opened. We will calculate the percentage of prescribed doses that appear to have been taken through week 6, 12 and 18. MEMS caps are considered the “gold standard” in

adherence research and show moderate validity with both patient populations (Gerson et al., 2004; Cramer et al., 1995).

**Electronic Health Record Adherence Indicators.** Many of the focal diagnoses have regular labs collected as part of usual clinical care. For example, medication trough levels are usually collected periodically for the purpose of therapeutic drug monitoring for AYA living with solid organ transplants (i.e., immunosuppressant medications) and epilepsy (i.e., anti-epileptic drugs.). For other diagnoses, regularly collected labs are considered partially indicative of adherence, such as the hemoglobin A1C test for type 2 diabetes and mean corpuscular volume/fetal hemoglobin for sickle cell disease.

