## **Design**

After passing eligibility screening and completing pre-treatment questionnaires, participants will be randomly assigned (1:1:1) to one of three 12-week groups: CPS delivered through voice-based phone calls (CPS-C), CPS delivered through text messaging (CPS-T), or automated text message reminders (Automated Reminders). A research colleague outside of the team used rand( ) function in Excel to create randomization blocks of 6 by sex assigned at birth and focal diagnosis. I hope to prevent substantial confounding by using stratified block randomization. For example, among the first 6 female participants with organ transplants, 2 would be assigned to CPS-C, 2 would be assigned to CPS-T, and 2 would be assigned to ATR.

The research colleague placed cards in sealed envelopes indicating the group assignment, and after the participant signed the consent form, the PI opened the envelope and informed the participant of the group they had been assigned to.

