## **Analytic Plan**

We will begin by examining the distribution and missingness of our outcome of interest, VAS. To take advantage of every available data point and account for repeated measures clustered within individual participants, we will run mixed-effect models in {STATA/SAS/R}, using a nested model-building process. If VAS is normally-distributed, we will specify linear mixed-effects models; otherwise, we may need to transform or dichotomize the outcome to ensure model assumptions are met. We will first run a simple model with only time (0, 6, 12, 18 weeks) as a Level I fixed effect predictor and VAS as a dependent variable, with the participant identification number included as a Level II random effect due to intra-individual correlation of VAS over time. Then, we will run increasingly complex models with intervention assignment (Cell Phone Support calls or texts n = 40 versus automated text reminders n = 20) included as a Level II fixed effect predictor, and then sex assigned at birth, focal medical diagnosis, medication complexity, age, and racial/ethnic identity as Level II fixed effect predictors, as well, to adjust for known or theoretical covariates. I will examine the impact of including increasing number of hypothesized predictors on model fit by examining AIC and  $R^2$ , and pare down the model if the model fit does not improve with all the hypothesized predictors included. This will lead to presenting parsimonious models that estimate the independent effect of the intervention on outcomes of interest, adjusted for all other predictors in the models. Finally, I will also assess whether model assumptions were met by plotting residuals versus fitted values. When I am

confident I have developed the most parsimonious, best-fitting model, I will calculate effect size estimates for the average difference in mean VAS between the Cell Phone Support call and text groups ( $n = 40$ ) and the automated text reminder group ( $n = 20$ ).

Then, we will follow the sample approach to predicting MEMS Caps adherence outcomes, and depression, social support, and self-efficacy. We will also run exploratory analyses using electronic-health record abstracted values (e.g., immunosuppressant levels, anti-epileptic drug levels, hemoglobin A1C, mean corpuscular volume/fetal hemoglobin) within focal diagnosis groups.

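### MEMS adherence has no week 0 value but is to be modelled like the VAS; prespecifying week 0 VAS as a covariate would recover some precision and guard against chance imbalance

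*Protocol*

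**What the plan says.** MEMS is listed in the protocol under Primary Outcomes: Adherence Dependent Variables. Participants "will be oriented to using MEMS caps for one of the medications they take daily of their focal diagnosis", and the score is defined at three times only: "We will calculate the percentage of prescribed doses that appear to have been taken through week 6, 12 and 18". No start date for the cap and no monitoring period before treatment is given. The Design section puts screening and questionnaires, but no cap period, ahead of allocation: "After passing eligibility screening and completing pre-treatment questionnaires, participants will be randomly assigned (1:1:1) to one of three 12-week groups".

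The Analytic Plan sets out the VAS model first: "We will first run a simple model with only time (0, 6, 12, 18 weeks) as a Level I fixed effect predictor". Intervention assignment is added next, and "then sex assigned at birth, focal medical diagnosis, medication complexity, age, and racial/ethnic identity as Level II fixed effect predictors". For MEMS it says only that "we will follow the sample approach to predicting MEMS Caps adherence outcomes" (*sample* is evidently a slip for *same*). Predictors may be pared down on AIC and R².

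The SAP's covariates are sex assigned at birth, diagnosis and age, each kept only if it improves fit. Its models and tables cover the six VAS measures, and MEMS does not appear. Both documents have the VAS collected at weeks 0, 6, 12 and 18.

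**The concern.** The VAS has a pre-treatment value and MEMS does not, so a plan written for one does not carry over unchanged to the other. For MEMS, the instruction leaves open which time points enter the model and what, if anything, stands in for adherence before treatment. Randomisation is stratified by sex and focal diagnosis, not by adherence, and no listed covariate measures it. With arms of 11 or 12, groups can easily differ by chance in how adherent they were at the start, and part of that difference carries into the MEMS comparison. A week 0 adherence measure is already collected and would go unused for this outcome. If its use is decided only after the MEMS results are seen, adjustment becomes a discretionary choice.

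**Working it through.** **Inputs from the documents.** Planned comparison 40 v 20 (Analytic Plan). Actual comparisons 23 v 11 and 12 v 11 (SAP; these are the VAS sample counts, as the number with usable MEMS data is not given). Effect size d = 0.85, within-person ICC 0.5 and three post-baseline measures (Power Analysis).

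**Assumed.** Two-sided 5% level. The correlation r between week 0 VAS and a later MEMS value is taken as 0.2, 0.3 and 0.5.

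**The plan's own figure.** The stated power of about 87% at d = 0.85 reproduces for 40 v 20 with one value per person: 87.4% by the normal approximation (86.3% by exact t). With the design effect the text describes, 1 + (3 − 1) × 0.5 = 2, the effective sizes are 60 v 30 and power is 96.7%. The single-value basis matches the stated figure and is the main basis below.

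**Chance baseline difference.** Its SD, in baseline SDs, is √(1/n₁ + 1/n₂):
- 40 v 20: √(0.0250 + 0.0500) = 0.27
- 23 v 11: √(0.0435 + 0.0909) = 0.37
- 12 v 11: √(0.0833 + 0.0909) = 0.42

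A gap above 0.3 SD in either direction has a probability of about 41% at 23 v 11 and 27% at 40 v 20.

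**How much reaches MEMS.** A fraction r of the gap carries over. At 23 v 11, a one-SD chance imbalance moves the MEMS difference by 0.2 × 0.367 = 0.07, 0.3 × 0.367 = 0.11 or 0.5 × 0.367 = 0.18 MEMS SDs.

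**Gain from the covariate, single MEMS value.** Residual variance is multiplied by 1 − r². Estimating the slope costs, in expectation, a factor 1 + 1/(N − 4) in variance, and the t quantile moves from N − 2 to N − 3 degrees of freedom. The ratio of CI widths is √[(1 − r²)(1 + 1/(N − 4))] × t(N − 3)/t(N − 2).

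At 23 v 11, N = 34: √(1 + 1/30) = 1.0165 and 2.0395/2.0369 = 1.0013, together 1.0178. At 12 v 11, N = 23: √(1 + 1/19) = 1.0260 and 2.0860/2.0796 = 1.0031, together 1.0291.

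| r | √(1 − r²) | width ratio, 23 v 11 | width ratio, 12 v 11 |
|---|---|---|---|
| 0.2 | 0.980 | 0.997 | 1.008 |
| 0.3 | 0.954 | 0.971 | 0.982 |
| 0.5 | 0.866 | 0.881 | 0.891 |

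Before the estimation cost, power at 23 v 11 and d = 0.85 goes from 64.0% with no covariate to 65.8%, 68.1% and 76.3% at the three values of r.

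**Mean of three MEMS values.** With ICC 0.5, equal correlations and the same r at each visit, the variance is (1 + 2 × 0.5)/3 = 2/3 without the covariate and 2/3 − r² with it. The cut is 6%, 14% and 38%, before estimation cost, so a repeated-measures analysis could gain more than the table shows.

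**The case against.** Three stronger readings are tempting, and the documents support none of them.

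- **That the MEMS analysis cannot be run as described.** It can. The approach is a nested mixed model with time, a participant effect, assignment and covariates. It fits on three time points by dropping one level. Neither the Analytic Plan nor the SAP tables show a time-by-group term, so the group term does not need a week 0 row.
- **That baseline imbalance makes the MEMS result biased or uninterpretable.** Randomisation makes the unadjusted comparison unbiased on average, and its standard error already allows for chance imbalance. Only a fraction r of any gap carries over.
- **That the protocol rules out a cap run-in.** It is silent. The absence is inferred from the order of steps in Design and from the MEMS description. The lack of a week 0 MEMS score is explicit.

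The other side has more. r is unknown and may be low: entry requires adherence below 80%, which narrows the baseline range; the cap covers one medication; and the protocol itself raises social desirability bias in self-report. At r = 0.2 there is no useful gain, and at 12 v 11 a slight loss. The section on exploratory analyses already concedes that stratification can fail in a small pilot and allows adjustment for measured covariates. The planned pre-post effect sizes name no outcome, so a MEMS change score is not expressly promised. All of this stands, and it limits the size of the point. It does not supply a prespecified MEMS model, and no passage names baseline adherence as a covariate.

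**Conclusion.** The point holds as an incomplete specification with a modest, inexpensive improvement available. It is not a threat to validity. The MEMS model needs its own time points, and the one pre-treatment adherence measure the trial holds should be assigned to it in advance. At 23 v 11 the expected benefit for a single MEMS value runs from nothing (r = 0.2) through about 3% (r = 0.3) to about 12% (r = 0.5) off the CI width. It also limits the effect of whatever imbalance actually occurred. This rests on the assumed range of r and on MEMS being available for roughly the SAP's VAS sample, although caps had to be mailed back at week 18.

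It also rests on week 0 VAS being completed before allocation was known. The opening of Design says so, but its later account ties the envelope only to consent ("after the participant signed the consent form, the PI opened the envelope"), so the order should be confirmed.

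**What to change.** In the protocol's Analytic Plan, and in the SAP if a MEMS analysis is added there, replace the cross-reference to the VAS approach with a MEMS specification that:

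1. fits the mixed model to weeks 6, 12 and 18 only, and says the time term has no pre-treatment point;
2. includes one named week 0 VAS item with one named recall period as a fixed covariate, retained whatever its effect on AIC or R²;
3. states that MEMS change from baseline cannot be reported.

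Before naming the covariate, reconcile the recall period: the protocol's VAS description gives the past 3 months, while SAP Tables 7 and 8 use the past week and past month.

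The cost is a few sentences and one degree of freedom, with no new data or visits. If r proves to be near 0.2, the price is an interval of essentially the same width at 23 v 11 and about 1% wider at 12 v 11. Because the SAP has no MEMS section at present, the text has to go in the Analytic Plan or wait for that section to be written.

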### ***Secondary Outcomes: Psychosocial Dependent Variables***

Participants were invited via text message to complete the following surveys at all four assessment periods., via RED Cap.

**Social Support.** Participants responded to the MOS Social Support survey to report on their perceived social support (Sherbourne & Stewart, 1991). There are three subscales that comprise the MOS: emotional/informational support, tangible support, and affectionate support.

**Self-Efficacy.** Three items assessed self-efficacy for taking medications as prescribed. The items included the following: “How sure are you that you can take the right amounts of your medicine at the right times?”; “How sure are you that you can do better with taking the right amounts of your medicine at the right times?”; and “How sure are you that you can take the right amounts of your medicine at the right times even if you were very tempted not to?” These items were scored using a 5-point Likert scale ranging from 1 (very sure I can) to 5 (very sure I cannot). For the current study, responses were reverse-coded and items summed to form a

composite self-efficacy score (max possible score = 15.0) as in (Kolmodin MacDonell et al., 2016).

**Depression.** We assessed depressive symptoms using the PHQ-9 (Kroenke et al., 2001).

## **Analytic Plan**

We will begin by examining the distribution and missingness of our outcome of interest, VAS. To take advantage of every available data point and account for repeated measures clustered within individual participants, we will run mixed-effect models in {STATA/SAS/R}, using a nested model-building process. If VAS is normally-distributed, we will specify linear mixed-effects models; otherwise, we may need to transform or dichotomize the outcome to ensure model assumptions are met. We will first run a simple model with only time (0, 6, 12, 18 weeks) as a Level I fixed effect predictor and VAS as a dependent variable, with the participant identification number included as a Level II random effect due to intra-individual correlation of VAS over time. Then, we will run increasingly complex models with intervention assignment (Cell Phone Support calls or texts n = 40 versus automated text reminders n = 20) included as a Level II fixed effect predictor, and then sex assigned at birth, focal medical diagnosis, medication complexity, age, and racial/ethnic identity as Level II fixed effect predictors, as well, to adjust for known or theoretical covariates. I will examine the impact of including increasing number of hypothesized predictors on model fit by examining AIC and  $R^2$ , and pare down the model if the model fit does not improve with all the hypothesized predictors included. This will lead to presenting parsimonious models that estimate the independent effect of the intervention on outcomes of interest, adjusted for all other predictors in the models. Finally, I will also assess whether model assumptions were met by plotting residuals versus fitted values. When I am

confident I have developed the most parsimonious, best-fitting model, I will calculate effect size estimates for the average difference in mean VAS between the Cell Phone Support call and text groups ( $n = 40$ ) and the automated text reminder group ( $n = 20$ ).

Then, we will follow the sample approach to predicting MEMS Caps adherence outcomes, and depression, social support, and self-efficacy. We will also run exploratory analyses using electronic-health record abstracted values (e.g., immunosuppressant levels, anti-epileptic drug levels, hemoglobin A1C, mean corpuscular volume/fetal hemoglobin) within focal diagnosis groups.

Finally, for exploratory purposes, we will calculate pre-post effect sizes for subgroups of interest to explore whether interventions are comparably efficacious by focal diagnosis, gender, and racial/ethnic identity. Stratification was used to reduce the variation in potential confounders to be spread similarly between conditions, but that is not always entirely successful, especially in a small pilot trial. Therefore, we will conduct exploratory analyses including measured covariates as potential confounders or effect modifiers in the model-building process.

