### **Power Analysis**

Using STATA SE Version 15 software, we estimated the statistical power achieved with our proposed sample, assuming the Cohen's  $d$  effect size of 0.85 between groups seen in our preliminary data, within-subject intra-class correlation of 0.5 for repeated measures. We used the

design effect for clustered data (3 post-baseline measures, intraclass correlation=0.5) to compute the effective sample size for each group. The table below shows estimated power to detect differences in CPS (combined) versus automated reminders, and for the comparison of CPS strategies (original vs live text) in the total sample and by medical condition. To be more conservative, we also provide the statistical power for the CPS comparisons with a smaller effect size of 0.75 and 0.50. We also computed power to detect simple pre/post (e.g., baseline-12 week) changes between groups. There is approximately 87% statistical power for group comparisons using the combined sample with the effect size of 0.85; power is reduced for subgroup comparisons and the smaller effect size. However, as this study is a pilot randomized trial, the sample is more than sufficient to estimate effect sizes and assess feasibility for use in future proposals. See Table 1 for details.

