Cell Phone Support to Promote Medication Adherence Among Adolescents and Young Adults With Chronic Illness

NCT04241627

8/8/2022

This randomized pilot trial tested three different digital health interventions against one another (CPS-C, n = 11, CPS-T, n = 12, and ATR, n = 11). We are interested in the impact on self-reported medication adherence. We have 6 different measures of dependent variables (VAS1w, VAS2w, VAS3w, VAS1m, VAS2m, VAS3m). We assessed our dependent variables 4 occasions, at 0 weeks (pre-tx), 6 weeks (mid-tx), 12 weeks (post-tx), and 18 weeks (follow-up). We would like to run mixed-effect models to test for intervention effects of 1) both CPS conditions (CPS-C and CPS-T, n = 23) versus ATR (n = 11); and 2) the CPS conditions against each other, ignoring ATR (CPS-C, n = 11 versus CPS-T, n = 12). I also have covariates (sex assigned at birth, diagnosis, age) that we can include during nested model building procedures, and include in final reported models if they lead to best fit.

Can we begin by examining the distributions of our dependent variables, and discuss whether we should use linear mixed-effects models; otherwise, we may need to transform or dichotomize the outcome or use a different type of model (poisson? Negative binomial?) to ensure model assumptions are met?

Then, can we evaluate the impact of missing data on my results by re-running these analyses using inverse probably weighting. It is possible that missing data will not be completely at random (i.e., participants with lower medication adherence may also be less likely to adhere to the online survey schedule).

Finally, I would like to calculate effect sizes for subgroups (see the final table). See tables on the next pages.

Blank Tables

Table 5

Best-Fitting Models Predicting Self-Reported Adherence for Both CPS Conditions (C and T) versus ATR (N = 34)

Dependent Variables	VAS1w			VAS2w			VAS3w			VAS1m			VAS2m			VAS3m		
	Estimates	CI	p															
Fixed Effects																		
Intercept																		
Time																		
Intervention Group (both CPS versus ATR)																		
Random Effects																		
σ^2																		
τ_{00}																		
τ_{11}																		
ρ_{01}																		
ICC																		
N																		
Observations																		
Marginal R ² / Conditional R ²																		
AIC																		

Note—Make ATR the reference group so the estimate tells us how the combined CPS groups compare

Table 6

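### Tables 5 and 6 treat the pre-randomisation week-0 VAS as an outcome and report a group main effect, which under the stated random-intercept model returns 0.75 of the average post-baseline effect

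*Protocol*

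**What the plan says.** The Protocol's Analytic Plan builds up from "a simple model with only time (0, 6, 12, 18 weeks) as a Level I fixed effect predictor and VAS as a dependent variable", with participant as the only random effect. The next step adds intervention (both CPS arms against ATR) as a participant-level fixed effect, followed by sex, diagnosis, medication complexity, age and race/ethnicity. The result to be reported is "effect size estimates for the average difference in mean VAS between the Cell Phone Support call and text groups" and the ATR group.

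The SAP keeps the four occasions: "We assessed our dependent variables 4 occasions, at 0 weeks (pre-tx), 6 weeks (mid-tx), 12 weeks (post-tx), and 18 weeks (follow-up". The fixed-effect rows of Table 5 are an intercept, time and "Intervention Group (both CPS versus ATR"; Table 6 has the same layout for CPS-T against CPS-C. The notes under both tables read that one row as the answer on how the groups compare.

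The week-0 value comes before allocation. The Design section says: "After passing eligibility screening and completing pre-treatment questionnaires, participants will be randomly assigned (1:1:1". The Power Analysis does not count it as an outcome, since it uses the "design effect for clustered data (3 post-baseline measures, intraclass correlation=0.5".

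**The concern.** A score taken before randomisation cannot carry a treatment effect. When it is one of the modelled outcomes and group enters only as a main effect, the coefficient averages a contrast whose expectation is zero with the three contrasts that can respond to treatment. The estimate is pulled towards the null.

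Covariates such as sex, diagnosis or age do not cure this. Only a group-by-time term, baseline VAS as a covariate or an equal-baseline constraint would, and neither document names any of these for the VAS models.

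Tables 5 and 6 carry the main efficacy results for all six VAS measures. The Protocol defends the pilot's size on the ground that "the sample is more than sufficient to estimate effect sizes and assess feasibility for use in future proposals". An effect size that is too low by construction works against that purpose and also makes a real effect harder to detect at N = 34.

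The Analytic Plan extends the same approach to depression, social support and self-efficacy, for which participants are invited to "complete the following surveys at all four assessment periods", so those analyses share the fault. MEMS adherence is defined through weeks 6, 12 and 18 with no week-0 value, so it does not.

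**Working it through.** **Inputs.** From the Power Analysis: d = 0.85, lower value 0.50, ICC 0.5, power about 87%. From the SAP: 23 v 11 (CPS v ATR) and 12 v 11 (CPS-T v CPS-C). Two-sided 5% is assumed, because the documents give no alpha.

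**The plan's own figure.** For 40 v 20 and one measurement per person, z = 0.85/√(1/40 + 1/20) = 3.10, and power = Φ(3.10 − 1.96) = 87%. A pre/post change gives the same result at ICC 0.5, since its variance is 2(1 − 0.5) = 1. Using the described design effect (1 + 2 × 0.5 = 2, effective n = 3n/2 = 1.5n) gives 97%. The 87% therefore fits a single-measure or pre/post calculation. The text refers to Table 1 for details, but that table is not in the available copy, so this goes no further.

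**What the coefficient estimates.** With a common time effect, the generalised least squares group coefficient is w′D. Here w = V⁻¹1/(1′V⁻¹1), and D holds the group differences at weeks 0, 6, 12 and 18. A random intercept makes V compound-symmetric, so each visit has weight 1/4 at any ICC:

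(0 + d6 + d12 + d18)/4 = 0.75 × mean(d6, d12, d18).

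This holds whatever the time pattern. A d of 0.85 becomes 0.6375.

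**Power.** Let k = 1/n₁ + 1/n₂, which is 0.1344 for 23 v 11 and 0.1742 for 12 v 11. With ICC ρ = 0.5, the variances are:
- planned four-visit main effect: (1 + 3ρ)/4 = 0.625k
- unadjusted post-baseline mean: (1 + 2ρ)/3 = 0.667k
- baseline-adjusted post-baseline mean: 0.667 − ρ² = 0.417k
- baseline-adjusted week 12 alone: 1 − ρ² = 0.75k

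For 23 v 11 the standard errors are 0.290, 0.299, 0.237 and 0.317. Noncentral-t power, with the planned effect taken as 0.75d:

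| Contrast | Planned | Post mean | Adjusted post mean | Adjusted week 12 |
|---|---|---|---|---|
| 23 v 11, d = 0.85 | 57% | 79% | 94% | 74% |
| 23 v 11, d = 0.50 | 24% | 37% | 53% | 33% |
| 12 v 11, d = 0.85 | 45% | 66% | 85% | 61% |

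Simulation (20,000 trials, 23 v 11, d = 0.85) gave 56.6%, 78.5%, 92.8% and 72.5%. The mean estimate was 0.635 for the planned model and 0.850 for the baseline-adjusted mean. Under the null the planned test rejected in 5.0% of 10,000 trials. At d = 0.85 and 23 v 11, planned against adjusted post-mean power is 69% v 92% at ICC 0.3 and 48% v 98% at ICC 0.7.

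**Missing follow-up** (assumed rates, missing at random, constant effect, ICC 0.5). With 10%, 20% or 30% missing independently at each follow-up visit, the factor is 0.72, 0.69 or 0.66. With monotone dropout at those rates per visit it is 0.67, 0.60 or 0.52.

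**Random slope.** The shells have rows for τ₁₁ and ρ₀₁. Take intercept and residual variances of 0.5 each, slope variance of 0.1 to 0.5 SD² at week 18, and ρ₀₁ from −0.7 to 0 (all assumed). The week-0 weight is then 0.15 to 0.41, so a constant effect is multiplied by 0.59 to 0.85. A second grid, with slope SD 0.01 to 0.05 per week and ρ₀₁ from −0.5 to 0.5, gave 0.37 to 0.81.

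**Chance imbalance at week 0.** The SD of the gap is √k, or 0.37 for 23 v 11 and 0.42 for 12 v 11. The planned coefficient carries 0.625 of it, an unadjusted post-baseline mean 0.5 and an adjusted one none. This is sampling error already in the standard error, not bias.

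**Knock-on for the next trial.** n per arm = 2(1.96 + 0.8416)²/d², which is 22 at d = 0.85 and 39 at d = 0.6375 (80% power). The ratio is 1/0.75² = 1.78.

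**The case against.** The best reply is that 0.75 is not a fixed property of Tables 5 and 6. The shells allow a random slope, and on the first grid above the sample-size factor then runs from about 1.4 (1/0.85²) to 2.9 (1/0.59²) for a constant effect. For an effect growing linearly from week 0, the multiplier is 0.48 to 0.91. Both documents also leave the model type open (transformed, dichotomised or count), and 0.75 belongs to the linear model. These points stand as limits on the number. They do not rescue the estimate: week 0 kept positive weight in every case tried.

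Second, Table 7 gives d, CI and p for baseline to week 12 in the total sample for both contrasts, and the Power Analysis mentions pre/post comparisons. This is a real safeguard, but a partial one. Table 7 is labelled exploratory and covers the past-week items only; Table 8, for past-month items, states no time span. The Analytic Plan still takes its effect size from the mixed model.

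Third, the shells omit covariate rows that the SAP permits, so a missing interaction row proves little by itself. That is fair, but the text lists the predictors to be added and group-by-time is not among them. The Protocol's later mention of effect modifiers concerns measured covariates in exploratory analyses.

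Fourth, not all of the power gain comes from removing dilution. The step from 57% to 79% does; the step from 79% to 94% is efficiency from baseline adjustment. The post-baseline average also includes week 18, six weeks after the 12-week intervention ends. Both points are correct, and the second is why visit-specific contrasts belong beside the average.

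Finally, the error is conservative. That is true of type I error, but it does not help a study whose product is an effect size.

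**Conclusion.** The concern holds. Followed as written, the plan mixes a pre-randomisation contrast into the main treatment estimate for all six VAS measures in both tables. The factor is 0.75 for a linear random-intercept model with complete data, and lower with missing follow-up under a constant effect. With a random slope it depends on variances that the documents do not give, so 0.75 is neither a floor nor a ceiling. At d = 0.85, ICC 0.5 and two-sided 5%, the planned test has 57% power for CPS v ATR and 45% for CPS-T v CPS-C, against 94% and 85% with baseline adjustment. There is no inflation of false positives. The analysis also disagrees with the power section, which counts three post-baseline measures. It should be corrected before Tables 5 and 6 are used as efficacy results or to plan a later trial.

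**What to change.** Model VAS at weeks 6, 12 and 18 with week-0 VAS as a covariate, or fit a constrained longitudinal model with a common baseline mean. Make the baseline-adjusted average post-baseline difference the main estimate; it fits the plan's averaged contrast and the three measures in the power section. Show the week-12 and week-18 contrasts from a group-by-time model beside it. Redraw the time and group rows of Tables 5 and 6 to match, and treat the depression, social support and self-efficacy surveys the same way.

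The cost is SAP wording and table shells; no new data are needed. There are a few more parameters at N = 34, and participants with no post-baseline VAS contribute only under the constrained model.
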